5.2 Statistical Analysis Plans

5.2.1 Analysis Sets

5.2.1.1 Safety Population (SP)

The Safety Population (SP) is defined as all randomized patients who received at least 1 dose of IMP and will be used for demographics and baseline characteristics, treatment exposure, concomitant medications, and all safety summaries. Patients in the SP will be included in the treatment group that they actually received, regardless of their randomized treatment.

5.2.1.2 Full Analysis Set (FAS)

The Full Analysis Set (FAS) is defined as all randomized patients and is also known as the intention-to-treat (ITT) set of patients. FAS will be used for all efficacy analyses. In addition, FAS will be also used for summary for disposition, demographics, and baseline characteristics. Patients in the FAS will be included in their randomized treatment group.

5.2.1.3 PK Concentration Population

The PK concentration population is defined as all patients in the safety population who have at least one non-missing PK assessment. These patients will be summarized for PK concentration summaries unless major protocol deviations identified during the protocol deviation review or if key dosing or sampling information is missing. PK concentration population will be used for PK concentration summary and listing.

5.2.2 Protocol Deviations

A full list of protocol deviations will be compiled and reviewed by the clinical team to identify key versus non-key deviations before final database lock. For deviations at study entry, patients will be assessed against the inclusion and exclusion criteria of the protocol. For on-study deviations, compliance with the protocol will be examined using blinded review of the database with regard to prohibited therapies, and timing and availability of planned assessments. The final list of protocol deviation will be approved by the study team prior to database lock and will be used to generate the PD deviation summary and listing.

5.2.3 Patient Disposition

The number of patients screened, randomized and included in each analysis population, along with study completion status, will be summarized by treatment group as well as overall. In addition, the number of patients who withdraw from the study and withdraw from IMP will be summarized by discontinuation reason.

Patient disposition will also be summarized for patients who are on simvastatin 40 mg/day or higher dose at any time during the study. The identification of these patients will be based on the concomitant statin medication use.

5.2.4 Demographic and Baseline Characteristics

The following demographic and baseline characteristics will be summarized by treatment group, as well as overall, for safety population and for FAS population: age (years), age will be summarized as a continuous variable and by age group (18-40, 41-64, 65-74, and ≥ 75), gender, race, ethnicity, height (cm), weight (kg), body mass index (kg/m^2), BMI group (< 25 , $25 - < 30$, $\geq 30 \text{ kg}/\text{m}^2$), Region (North America, and EU), systolic and diastolic blood pressure (mmHg), fasting lipid parameters (TC [mg/dL], calculated LDL-C [mg/dL], HDL-C [mg/dL], non-HDL-C [mg/dL] and TGs [mg/dL]), apoB (mg/dL), hsCRP (mg/dL), stratification factors: ASCVD only/HeFH (with or without ASCVD), and baseline statin intensity (low, moderate, high), history of diabetics and hypertension, eGFR category, tobacco history, alcohol history, and weekly average number of alcoholic drinks. Data will be summarized using descriptive statistics for continuous variables and using counts and percentages for categorical variables by treatment group and overall. Demographic and baseline characteristics will be summarized for patients who are on simvastatin 40 mg/day or higher dose at any time during the study.

The baseline estimated glomerular filtration rate (eGFR) categories are: normal: $\geq 90 \text{ mL}/\text{min}/1.73\text{m}^2$; mild Renal Impairment: $60-89 \text{ mL}/\text{min}/1.73\text{m}^2$; moderate Renal Impairment: $30-59 \text{ mL}/\text{min}/1.73\text{m}^2$, and severe Renal Impairment ($15-29 \text{ mL}/\text{min}/1.73\text{m}^2$).

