## 7.2. Subject Exclusion Criteria

Patients who meet any of the following criteria will not be randomized:

1. Total fasting triglyceride  $\geq 500 \text{ mg/dL}$  ( $5.6 \text{ mmol/L}$ ) at Week -2 (Visit S1)

Note: TG may be repeated 1 time with the screening period extended up to 2 weeks. For those patients who have a repeat TG, the mean of the first value and the repeat value will be used to determine eligibility.

2. Renal dysfunction or nephritic syndrome or a history of nephritis, including eGFR (using central laboratory determined Modification of Diet in Renal Disease [MDRD] formula)  $<30 \text{ mL/min}/1.73 \text{ m}^2$  at Week -2 (Visit S1) [1].

Note: At the discretion of the investigator, the screening period may be extended up to 2 weeks for a single repeat eGFR. For those patients who have a repeat eGFR, the repeat value will be used to determine eligibility.

*Note: Also excluded are renally impaired patients receiving an average daily dose of simvastatin 40 mg with eGFR below  $<45 \text{ mL/min}/1.73 \text{ m}^2$ .*

3. Body mass index (BMI)  $\geq 50 \text{ kg}/\text{m}^2$
4. Concomitant use of simvastatin *at average daily doses greater than 40 mg.*
5. *Concomitant use of a PCSK inhibitor (Praluent® [alirocumab] or Repatha® [evolocumab]) at Week -2 (Visit S1) or prior use of a PCSK9 inhibitor within the past 4 weeks of Week -2 (Visit S1) will be excluded from this study.*

*Note: Patients are allowed to initiate a PCSK9 inhibitor as adjunctive therapy at Week 24 if the LDL-C threshold criteria have been met as described in Section 11.1.6.3.5.*

6. Recent (within 3 months prior to the screening visit [Week -2 (Visit S1)] or between screening and randomization visits) MI, unstable angina leading to hospitalization, uncontrolled, symptomatic cardiac arrhythmia (or medication for an arrhythmia that was started or dose changed within 3 months of screening), CABG, PCI, carotid surgery or stenting, cerebrovascular accident, transient ischemic attack (TIA), endovascular procedure or surgical intervention for peripheral vascular disease or plans to undergo a major surgical or interventional procedure (eg, PCI, CABG, carotid or peripheral revascularization). Patients with implantable pacemakers or automatic implantable cardioverter defibrillators may be considered if deemed by the Investigator to be stable for the previous 3 months.

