5.4.6 Laboratory Evaluations

Continuous laboratory parameters (serum chemistry, hematology, coagulation (only at screening after amendment 3 and for those patients receiving anti-coagulation), urinalysis, urinalysis [microscopic]) listed in Table 4; fasting serum glucose, and HbA1c will be summarized using descriptive statistics for the observed value and the change from baseline by history of diabetics. Missing values for any of the laboratory evaluations will not be imputed; that is, only observed case data will be used. Baseline is defined as the last value prior to the first dose of study medication. Categorical urinalysis data will be listed, but will not be summarized.

As part of the AESI evaluation, below safety lab abnormality will be summarized by treatment group. All post-baseline lab values are being considered. Further details are provided in Section 5.4.6.1 through 5.4.6.4.

- ALT or AST (> 3x ULN and >5xULN)
- TB (> 2x ULN)
- Potential Hy's Law case: (ALT and/or AST > 3xULN with concurrent TB > 2xULN)
- CK (> 5x ULN) and (>10x ULN)
- Fasting Serum Glucose (mg/dL) (≤ 50 , and ≥ 126) by history of diabetics
- HbA1C ($\geq 6.5\%$) by history of diabetics
- Creatinine (change from baseline for >1 mg/dL)
- eGFR (< 15 mL/min/1.73m², 15 < 30 mL/min/1.73m²)
- Hgb (g/dL) (decrease from baseline for ≥ 2 g/dL)
- Hgb (<8 g/dL)

Table 4: Clinical Laboratory Parameters (Safety)

Hematology 
 • Hematocrit (Hct) • Hemoglobin (Hgb) • Mean corpuscular hemoglobin (MCH) • Mean corpuscular hemoglobin concentration (MCHC) • Mean corpuscular volume (MCV) • Platelet count • Red blood (RBC) cell count • White blood (WBC) cell count with differential (absolute and %) 	Blood Chemistry (serum, fasting) 
 • Albumin (Alb) • Alkaline phosphatase (Alk-P) • Alanine aminotransferase (ALT; SGPT) • Aspartate aminotransferase (AST; SGOT) • Blood urea nitrogen (BUN) • Calcium (Ca) • Carbon dioxide (CO₂) • Chloride (Cl) • Creatinine • Creatine kinase (CK) • Glucose • Lactate dehydrogenase (LDH) • Phosphorus • Potassium (K) • Sodium (Na) • Total and direct bilirubin (TB) • Total protein • Uric acid

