5.4.6.2 Musculoskeletal Safety

CK levels will be summarized by the value and change from baseline in the value, by treatment group and visit as well as baseline eGFR category. In addition, the number and percent of patients with abnormal CK values ($> 5 \times \text{ULN}$, $> 10 \times \text{ULN}$) will be summarized for overall safety population and patients who were on simvastatin 40mg or higher dose at any time during the study. These summaries of patients with abnormal CK will be performed overall, normal baseline CK, and abnormal baseline CK.

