5.4.6.4 Renal Safety

By-visit summary and shift tables of eGFR by baseline category will be provided by treatment group.

In addition, renal function abnormality will be identified as: (1) A creatinine change from baseline of $> 1 \text{ mg/dL}$ (2) eGFR value $< 30 \text{ mL/min/1.73m}^2$. A shift table from baseline with the number and percent of patients using the two categories will be presented.

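### SAP 5.2.4 puts eGFR 30–59 in a single category, so no planned eGFR shift or eGFR-threshold table marks a fall within that band as worsening, and CK cannot be seen separately for patients entering at 30 to <45

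*SAP*

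**What the plan says.** SAP 5.2.4 sets out the renal bands after the words "The baseline estimated glomerular filtration rate (eGFR) categories are: normal": 90 or more is normal, 60–89 mild, 30–59 moderate and 15–29 severe. No other set of eGFR categories is defined in the SAP.

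Three analyses bear on renal function:

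- SAP 5.4.6.4: "By-visit summary and shift tables of eGFR by baseline category will be provided by treatment group".
- SAP 5.4.6.4 also defines a renal abnormality by two criteria, a creatinine change from baseline above 1 mg/dL and an eGFR below 30, and adds: "A shift table from baseline with the number and percent of patients using the two categories will be presented". SAP 5.4.6 uses the same creatinine cut-off and divides low eGFR into 15 to <30 and <15.
- SAP 5.4.6.2, where the grouping is again by band: "CK levels will be summarized by the value and change from baseline in the value, by treatment group and visit as well as baseline eGFR".

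Protocol 7.2, criterion 2, sets the general entry limit at eGFR 30. The figure 45 appears there only as the limit in a note that begins: "Also excluded are renally impaired patients receiving an average daily dose of simvastatin 40 mg with eGFR below". Protocol 8.2.2 now lists simvastatin at 40 mg/day or more as prohibited. The on-study withdrawal level in Protocol 11.1.6.3.2 is 15.

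**The concern.** Safety is the primary objective, and renal and muscle events are among the SAP's events of special interest (Appendix 2). The eGFR shift table is where a reader will look for patients whose kidney function worsened. With one band covering 30 to 59, that table records a large fall inside the band as no change.

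The same band limits the muscle analysis. The CK summary is the only muscle-safety table in the SAP broken down by baseline eGFR: muscle-related adverse events (5.4.3) are not, and eGFR is not among the subgroups in 5.2.5. A patient entering at 32 and one entering at 58 share a row, so CK behaviour at the lower end of the admitted range cannot be read from the planned output.

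**Working it through.** The plan states no figure to reproduce here. The check applies the SAP's own rules to a worked case, a fall from 55 to 34 mL/min/1.73 m².

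**Inputs.** Bands from SAP 5.2.4; eGFR cut-offs <30, 15 to <30 and <15, and creatinine change >1 mg/dL, from SAP 5.4.6 and 5.4.6.4. The protocol names the MDRD formula but gives no coefficients, so the link between eGFR and creatinine is an assumption: eGFR proportional to creatinine^(−k), with k from 1.0 to 1.2.

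**1. Size of the fall.** (55 − 34) / 55 = 21 / 55 = 38%.

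**2. Category shift.** 55 and 34 both lie in 30–59. The patient is moderate at both times and sits on the diagonal of the shift table.

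**3. eGFR cut-offs.** 34 is not below 30, so none of the thresholds is met.

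**4. Creatinine flag.** The implied ratio of creatinine values is r = (55/34)^(1/k), and the rise is baseline × (r − 1). The flag needs baseline > 1 / (r − 1).

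| k | r | Baseline needed for rise >1 mg/dL | Rise at baseline 0.9 | Rise at baseline 1.5 |
|---|---|---|---|---|
| 1.0 | 1.618 | 1/0.618 = 1.62 mg/dL | 0.56 | 0.93 |
| 1.2 | 1.493 | 1/0.493 = 2.03 mg/dL | 0.44 | 0.74 |

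For assumed baselines of 0.9 to 1.5 mg/dL the rise is 0.44 to 0.93 mg/dL, so the flag is missed.

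**5. How the bands rank change.** The widest fall inside the moderate band, 59 to 30, is 29/59 = 49% and shows no shift. A fall from 60 to 59 is 1/60 = 1.7% and shows one.

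**6. After a split at 45.** 55 falls in 45–<60 and 34 in 30–<45, so the fall appears as a one-category worsening.

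**7. What the split leaves.** Falls of 89 to 60 (29/89 = 33%) and 44 to 30 (14/44 = 32%) still show no category shift.

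**The case against.** The strongest reply is that the fall does not vanish from the output, and most of that reply stands.

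- The by-visit eGFR summary includes the value. Under SAP 5.1 the default statistics include the quartiles, minimum and maximum, so extreme values are visible. These statistics do not count how many patients fell, or by how much.
- SAP 5.4.6 counts patients with out-of-range results for each laboratory parameter at each time point, and creatinine is one of them. The patient may well be counted there, although the documents give no normal limits. Someone already out of range at baseline would look unchanged.
- SAP Appendix 2 includes terms for decreased filtration rate and increased creatinine, so the fall counts as a renal event if the investigator reports it.

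A reader might infer that such a patient appears in no renal table. The documents do not support that. The accurate statement is that no eGFR shift or eGFR-threshold table marks the fall as worsening.

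A reader might also take 45 as the protocol's general renal risk boundary. It is not. In the current text it applies only to patients on simvastatin 40 mg/day, whose adverse events, liver tests and CK the SAP summarises separately. The general protocol levels are 30 for entry and 15 for withdrawal, and the SAP's <30 and <15 cut-offs correspond to those.

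Nor does the SAP's summary of changes, which records that the categories were altered to include 30 to <45, show that a separate category was intended and then lost. It fits equally well with extending the moderate band down to 30.

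Finally, any fixed band hides some falls. That is true, and it limits what the fix can achieve.

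**Conclusion.** The point holds as a limitation of the planned tables. It is not an error or a contradiction. With 30–59 as one category, a fall such as 55 to 34 (38%) is shown as no shift, meets no eGFR cut-off, and reaches the creatinine flag only from a baseline above about 1.6 to 2.0 mg/dL. Patients entering at 30 to <45 have no row of their own in the CK summary.

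Two things rest on assumption: the range k = 1.0 to 1.2 and the illustrative creatinine baselines. The category and eGFR cut-off results need neither. The shift-table result does rest on reading the category in 5.4.6.4 as the one defined in 5.2.4, which is the only definition given. The number of patients affected cannot be derived from the documents. The change is worth making because it is cheap and serves the primary safety objective; no planned test depends on it.

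**What to change.** In SAP 5.2.4, divide the moderate band into 45 to <60 and 30 to <45 mL/min/1.73 m², for both baseline and post-baseline values. Use the divided bands in the eGFR shift tables (5.4.6.4) and in the CK summary by baseline eGFR (5.4.6.2), and keep 30–59 as a subtotal so that nothing now planned is lost.

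The cost is a change of SAP wording and an extra category in each table. No new data are needed, because safety chemistry is drawn at every main visit and a by-visit eGFR summary is already planned. The 30 to <45 cell may be small, which is tolerable in a descriptive table. Falls within any one band will remain unmarked. If proportional decline is itself of interest, a percent-decline category for eGFR would address it directly.

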5.2.5 Subgroup Variables

Subgroups defined by below variables will be evaluated for safety and the LDL-C efficacy endpoint.

- 1) Gender (male vs. female)

Confidential

Page 17 of 33

- 2) Age (< 65 yrs. vs. \geq 65 yrs. and < 75 yrs. vs. \geq 75 yrs.)
- 3) Baseline CVD risk category (HeFH (with/without ASCVD) vs. ASCVD only)
- 4) Baseline statin intensity (low vs. moderate vs. high)
- 5) Race (White vs. other)
- 6) Baseline LDL category (< 100 mg/dL vs. \geq 100 mg/dL) (efficacy only)
- 7) History of diabetes (yes vs. no)
- 8) Body Mass Index (BMI) (< 25, 25 - < 30, \geq 30 kg/m²)
- 9) Region (North America, EU)

In case the number of patients within a subgroup is too small, e.g. less than 5% of the overall population, the analyses may not be performed or the subgroup levels may be combined.

5.2.6 Medical History

General medical history, and cardiovascular history/risk factors will be summarized by treatment group, as well as overall, for FAS population and presented in a by-patient listing. Where appropriate, terms will be coded using the Medical Dictionary for Regulatory Activities (MedDRA) Version 18.1 or later.

5.2.7 Baseline Serology, Serum and Urine Pregnancy Test and TSH

Hepatitis B surface antigen (HBsAg), hepatitis C virus (HCV), and serum pregnancy test (only for females of childbearing potential), follicle stimulating hormone ([FSH], only for females who are < 55 years old and > 1 year without menses), urine pregnancy test Day 1 prior to randomization (only in Canada for females prior to amendment 3 and in all women who are of childbearing potential after amendment 3, and thyroid-stimulating hormone (TSH) will be presented in a by-patient listing.

5.2.8 Prior and Concomitant Medications

Prior medications are defined as medications that ended prior to the initiation of double-blind IMP. Concomitant medications are defined as medications that were ongoing at the time of double-blind IMP initiation or new medications that started post double-blind IMP initiation and within 30 days following the date of the last dose of IMP.

Medications, including prior statin medications, will be coded using WHO Drug (March, 2015, or later). The use of prior or concomitant medications will be summarized by treatment group, as well as overall, for the safety population according to Anatomical Therapeutic Chemical (ATC) class and coded medication name. Statin medications will be summarized separately. Prior and concomitant medications will be listed for each patient.

Number of patients receiving additional (post-randomization) adjunctive lipid-modifying therapy will be identified by medication class and will be summarized by the reasons for their additional treatment (hyperlipidemia or. hypertriglyceridemia) per concomitant medication CRF.

5.2.9 IMP Exposure and Compliance

The length of exposure to IMP (ETC-1002 or placebo) will be calculated as the number of days from the first dose of double-blind IMP to the last dose of double-blind IMP, regardless if the patient missed one or more doses of IMP. Length of exposure will be summarized by treatment group using descriptive statistics for the safety population.

The number and percentage of patients who were compliant with taking IMP will be summarized by treatment group for the safety population for the following categories 0- $<80\%$; $\geq 80\%$.

Overall compliance will be calculated as: $100 * (\text{Total Number of Tablets Dispensed} - \text{Total Number of Tablets Returned}) / (\text{Treatment Duration in Days})$. The IMP administration and compliance data, including reasons for poor compliance, if noted in CRF will be listed for each patient.

5.3 Primary Efficacy Endpoints and Analyses

For all efficacy analyses, the FAS will be used, with patients included in their randomized group, regardless of the treatment they actually received.

The primary and key secondary efficacy endpoints will be included in a step-down testing procedure to control overall type I error. Below endpoints will be tested sequentially at alpha level of 0.05. Each endpoint will be tested only if the previous endpoint achieved statistical significance.

1. percent change from baseline to Week 12 in LDL-C (primary efficacy)
2. percent change from baseline to Week 24 in LDL-C
3. percent change from baseline to Week 12 in non-HDL-C
4. percent change from baseline to Week 12 in TC
5. percent change from baseline to Week 12 in apoB
6. percent change from baseline to Week 12 in hsCRP

The clinical hypothesis being tested for each respective endpoint is that a treatment regimen with bempedoic acid 180mg daily in addition to other lipid modifying therapies (including statin) will result in higher reduction in respective lipid value than that from the lipid modifying therapy alone.

5.3.1 Analysis for the Efficacy Parameters

Percent change in LDL-C, non-HDL-C, TC, and apoB at week 12 or week 24 will be analyzed using the analysis of covariance (ANCOVA) method. The ANCOVA model will include treatment, randomization stratum (from IWRs) as factors, and baseline value as covariate. In case of number of subjects within a stratum is too small for a meaningful analysis, the strata may be combined to obtain larger cell size. To account for the likelihood of unequal variances between the treatment groups, the ANCOVA model will be implemented within mixed model framework and the <repeated/group=> option will

be used to allow estimating the residual variances separately between the groups. The model assumptions for ANCOVA will be assessed and if these assumptions are severely violated, alternative non-parametric approach will be performed.

An example sas code for ANCOVA analysis is shown as below:

```
PROC MIXED DATA=adeff;
  class armcd stratum;
  model chg = blres armcd stratum/ solution ddfm=kenwardroger;
  repeated /group=armcd;
  lsmeans armcd / diff=control ('0') cl;
```

For hsCRP, a non-parametric (Wilcoxon rank-sum test) analysis with Hodges-Lehmann estimates and confidence interval will be performed because based on historical knowledge, publication precedence (Brendan et al., 2006) and recent data available, hsCRP is known to be skewed by extreme values and have non-normal distribution.

Efficacy data (actual value, change and percent change from baseline) from all visits will be presented using descriptive statistics using both conventional and standard units. A figure of mean (+/- SE) value or median (IQR) as appropriate, over time will be provided for these efficacy parameters.

